6.2 Data collection

Only real-world retrospective data will be used for this study. Deidentified retrospective data will be transcribed into the eCRF system from source data at each clinical site or from existing COVID-19 cohort databases, where appropriate. No personal identifiable data will be transmitted to NEAT ID. The data elements will be transcribed from source data according to the data collection list below. Mechanisms to ensure data quality and integrity will be deployed as per applicable standard operating procedures and in line with GCP and GPP. Patients and controls will be identified and documented by participating sites, provided unbiased matching for inpatient/outpatient status at the time of COVID-19 diagnosis is ensured. Alternatively, and to avoid potential site-related bias during selection of HIV negative controls with COVID-19 diagnosed in hospital, data from matched controls will be obtained from appropriate existing COVID-19 cohort databases, e.g. LEOSS (Lean European Open Survey on SARS-CoV-2 infected patients) or ISARIC (International Severe Acute Respiratory and emerging Infection Consortium).

For all patients the following information will be collected:

- Age
- Sex
- Ethnicity (where available)
- Comorbidities (see appendix 1)
- Weight (kg) and height (m) (to calculate BMI)

For patients with COVID-19 the following information will be collected (where applicable):

- Date of positive PCR test result (documented or patient-reported)
- COVID-19 diagnosis inpatient or outpatient
- All-cause mortality in hospital, or palliative discharge, or mortality at 6 weeks after diagnosis of COVID-19 or at discharge from hospital
- Hospitalisation for COVID-19 and length of hospitalisation
- Critical care admission (high dependency unit or intensive care unit) for COVID-19 and length of stay in critical care
- Length of invasive ventilation
- Length of extracorporeal membrane oxygenation (ECMO)
- Need for kidney replacement therapy
- Inflammatory markers and blood cell counts at COVID-19 diagnosis¹ (if available):
 - Full blood cell count (Platelet count, RBC Count, WBC count (absolute), Haemoglobin, Haematocrit, MCV, MCH, Neutrophils, Lymphocytes, Monocytes, Eosinophils, and Basophils), ALT, AST, total bilirubin, urea, serum creatinine, calcium, glucose and HbA1C levels, total cholesterol, triglycerides, CRP, D-dimer, ferritin, and lactate dehydrogenase

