7.3.2 Primary outcome analysis

The first primary outcome analysis will be performed on PLWHIV with COVID-19 versus HIV uninfected individuals with COVID-19. The endpoint is the occurrence of critical care admission (high dependency unit or intensive care unit), mortality in hospital or palliative discharge when discharged from hospital, or mortality at 6 weeks after diagnosis of COVID-19 or at discharge from hospital (where applicable). Kaplan-Meier estimates will be used to estimate the proportion of participants with the primary endpoint events. Unadjusted and adjusted hazard ratios (HR) will be estimated using the Cox proportional hazard model to assess the impact of HIV-infection on the severity of COVID-19. The validity of the proportionality assumption will be assessed and tested. The adjusted variables will be the following (potential confounders): Age (<60 vs 60-64 vs 65-69 vs 70-74 vs ≥75 years); Sex at birth (female vs male); Obesity (BMI>30 kg/m²); and Comorbidities (see appendix 1).

The second primary outcome analysis will be performed within the group of PLWHIV (PLWHIV with COVID-19 versus PLWHIV without COVID-19). The endpoint is to assess factors associated with severe COVID-19 within the group of PLWHIV. Conditional logistic regression models will be used to account for the case-control matching. The following variables will be assessed: Age (<60 vs 60-64 vs 65-69 vs 70-74 vs ≥75 years); Sex at birth (female vs male); Obesity (BMI >30 kg/m²); Comorbidities (see appendix 1); time since HIV diagnosis (years); current ART; CDC disease stage; CD4 cell nadir; last CD4 cell count/HIV-RNA before COVID-19 diagnosis (including CD4% and CD4/CD8 ratio) at baseline. For continuous variables, the decision to treat the variable as a continuous or categorical variable (as tertile) will be based on the lowest Akaike information criterion value for the corresponding univariable conditional logistic regression analysis. Variables achieving P < 0.20 in the univariable analysis will be retained for the multivariable analysis.

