7.3.3 Secondary outcome analysis

All secondary outcome analysis will be performed on PLWHIV with COVID-19 compared to HIV uninfected individuals with COVID-19.

The proportion of hospitalised patients for COVID-19, the length of stay in hospital, the length of stay on ICU, the length of extracorporeal membrane oxygenation (ECMO), and the proportion of participants with a need for kidney replacement therapy will be estimated using the Kaplan-Meier estimate. Unadjusted and adjusted hazard ratios (HR) will be estimated using the Cox proportional hazard model to assess the impact of HIV-infection on the severity of COVID-19. The adjusted variables will be the same as those used for the first primary outcome analysis.

The number of ventilator-free days (VFDs) will be compared between groups using competing risk regression, with extubation and mortality a competing event, adjusted for potential confounders.

Linear regression models will be used to compare Charlson Comorbidity Index (CCI), the age-adjusted CCI (ACCI), 30-day mortality index after COVID infection, inflammatory marker and blood cell counts at COVID-19 diagnosis between the 2 groups, adjusted for potential confounders. The sample size will be quite large to consider CCI, 30-day mortality index, inflammatory marker and blood cell counts as normally distributed variables.

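### As the plan reads, the Charlson indices (CCI, ACCI) are adjusted for their own components, so the modelled group difference is forced to or near zero; the claim that a large sample makes variables normal is also wrong.

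*Combined protocol and SAP*

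**What the plan says.** - **Model for the indices and markers (7.3.3).** "Linear regression models will be used to compare Charlson Comorbidity Index (CCI), the age-adjusted CCI (ACCI), 30-day mortality index after COVID infection", together with inflammatory markers and blood counts at diagnosis, "between the 2 groups, adjusted for potential confounders". For the Cox models the same section asks for unadjusted and adjusted estimates. For the linear models it names only the adjusted comparison.
- **Meaning of the covariate label (7.3.2).** "The adjusted variables will be the following (potential confounders" introduces a list of age in five bands, sex at birth and obesity, ending with "and Comorbidities (see appendix 1". No other set in the document carries this label, and no exception is made for outcomes that are themselves comorbidity scores.
- **Source of the indices (6.2).** The only comorbidity item collected is "Comorbidities (see appendix 1".
- **Distributional statement (7.3.3).** "The sample size will be quite large to consider CCI, 30-day mortality index, inflammatory marker and blood cell counts as normally distributed variables". No transformation, robust variance, alternative model or residual check is mentioned.
- **Markers (6.2).** These include "CRP, D-dimer, ferritin, and lactate dehydrogenase", taken where available.

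**The concern.** Secondary endpoint 7 is total comorbidity burden measured by CCI and ACCI. If the items that make up the score are also covariates, the model asks whether the score differs between groups among people with the same comorbidities. The answer is close to no whatever the data show. A reader of the results could take an adjusted difference near zero as evidence that the groups carry the same burden, when the model alone produced it.

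The normality statement raises a separate and smaller issue. It treats a large sample as a reason not to think about the shape of the outcome. For right-skewed laboratory markers, a difference in raw means depends heavily on a few extreme values, and real differences become harder to detect.

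**Working it through.** **1. The plan's own figure.** Table 1 in 7.1 is the only calculation behind the large-sample statement. For hospitalisation at a hazard ratio of 1.3:

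- Events = 1500 × 0.35 + 500 × (1 − 0.65^1.3) = 739.4.
- The Freedman formula with allocation ratio φ = 1/3 gives power = Φ(√739.4 × √φ × 0.3 / (1 + 1.3φ) − 1.96) = 90.8%. The table states 90.
- Death at 1.5 gives 85.4%, against 85 in the table.

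Table 1 therefore reproduces, but it covers only time-to-event severity outcomes. Nothing in 7.1 addresses the indices or markers.

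**2. Adjusting an index for its components.** Write the index as CCI = Σ wₖCₖ, where Cₖ are the Appendix 1 items at their scored level. Regress it on group and all Cₖ. The coefficients (group = 0, each item = wₖ) fit with zero residual, so least squares returns exactly that solution and R² = 1.

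| Simulated case (500 vs 1500) | True difference | Adjusted difference |
|---|---|---|
| Weighted sum, items at 10% vs 6% prevalence, all items as covariates | 1.16 | 0.00 (R² = 1.0) |
| Same, adjusted only for the number of items present | 1.16 | about 0.00 |
| Ten graded conditions at 18% vs 10%, entered only as yes/no, same severity mix in both groups | 1.35 | about 0.00 |

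Prevalences and weights are assumed, because the documents give neither. The third row shows that coarser coding does not rescue the estimate. Only group differences in severity within a condition would survive it.

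ACCI adds an age part. Age is a covariate too, in the bands of 7.3.2, so most of that part is also removed. Any remainder would come from age differences within a band, and controls are already matched to within 5 years of age.

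**3. Sample size and skewness.** For a log-normal variable with log-SD 1.0 the population skewness is 6.2. Median sample skewness was 3.1, 3.9 and 4.5 at control-group sizes of 150, 450 and 1500. A larger sample estimates the skew better; it does not remove it.

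**4. Validity of the raw-scale test.** In 4,000 simulated datasets per setting at 500 versus 1500, type I error of the raw-scale t-test was 4.5% to 5.4% for log-SDs from 0.5 to 1.5.

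**5. Power of the raw-scale test.** Assume log-normal markers, values 30% higher in cases, 500 versus 1500, two-sided 5%, and control mean set to 1.

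- Coefficient of variation: cv = √(exp(s²) − 1), where s is the log-SD.
- Raw scale, unequal-variance SE: cv × √(1.69/500 + 1/1500) = 0.0636 × cv.
- Raw scale, pooled SE: cv × √[(500 × 1.69 + 1500)/2000] × √(1/500 + 1/1500) = 0.0559 × cv.
- Log scale SE: s × √(1/500 + 1/1500) = 0.0516 × s. The effect is ln 1.3 = 0.262.
- Power ≈ Φ(effect/SE − 1.96).

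| s | cv | Raw z (unequal, pooled) | Raw power | Log z | Log power |
|---|---|---|---|---|---|
| 1.0 | 1.311 | 3.60, 4.09 | 95–98% | 5.08 | >99% |
| 1.25 | 1.942 | 2.43, 2.76 | 68–79% | 4.06 | 98% |
| 1.5 | 2.913 | 1.62, 1.84 | 37–45% | 3.39 | 92% |

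At s = 0.75 both scales exceed 99%, so with mild skew the choice costs almost nothing for this effect. For a smaller, 1.2-fold shift, simulated power was 81% raw against 95% log at s = 1.0, and 49% against 81% at s = 1.25.

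**The case against.** **The covariate overlap is an inference.** The sentence in 7.3.3 that carries over the primary-analysis covariates belongs to the Cox paragraph. The linear-model sentence uses only the general label. That is correct, and the defect could equally be called an under-specified covariate list. But 7.3.2 is the only place that gives the label content, so an analyst following the plan would use that set.

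**The comorbidity objective is only descriptive.** A reader might infer that the study cannot describe comorbidity burden at all. The documents do not support that: 7.3.1 plans means, medians and quartiles for all continuous variables, and these crude summaries are untouched. What is lost is the planned modelled comparison.

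**The VACO index.** A reader might infer that the 30-day mortality index suffers in the same way. The protocol says only that it is estimated from health status before COVID-19. Its inputs are not listed, so overlap with the covariates cannot be shown here.

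**The normality sentence can be read charitably.** It may be shorthand for large-sample inference on means, and the type I error results support that reading. A mean difference is also a legitimate estimand, and the planned medians and quartiles will make any skew visible. All of this stands. A stronger reading, that the linear-model tests are invalid, is not supported. The absence of a transformation is likewise inferred from silence, and whether the indices should instead have an ordinal or count model is a matter of preference.

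**Conclusion.** The main point holds: with the covariate set of 7.3.2, the adjusted group difference in CCI is exactly zero if all components enter at their scored level, and near zero under coarser coding unless severity within conditions differs between groups. ACCI is affected in the same way and also loses most of its age part. This rests on reading the label in 7.3.3 as the set defined in 7.3.2, and on the indices being built from Appendix 1, the only source collected. It concerns secondary endpoint 7 and leaves the primary analyses alone.

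The secondary point holds as a wrong justification with a conditional cost. Error rates stay close to nominal. Power falls materially only if the markers are strongly skewed: for a 30% difference, little is lost at log-SD 1.0, while at 1.5 power drops from about 92% to 37–45%. Log-normality and these log-SDs are assumptions, since the documents give no distribution for any marker. The figures also use the full 500 and 1500; markers are collected only where available, so actual numbers may be lower.

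**What to change.** 1. In 7.3.3, state the covariates for each linear model. When CCI or ACCI is the outcome, leave out the Appendix 1 comorbidities, and for ACCI leave out age as well.
2. For the 30-day mortality (VACO) index, leave out any covariate that is an input to the index, after listing those inputs.
3. Delete the sentence on normality.
4. Prespecify log-scale analysis for right-skewed markers such as CRP, D-dimer and ferritin, reporting geometric mean ratios with confidence intervals.

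The cost is wording in the analysis plan, with no new data. The one small downside is that the marker estimate becomes a ratio of geometric means rather than a difference in means; the crude summaries of 7.3.1 still report the raw means.

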7.4 Subject population

All eligible subjects with a matching individual will be included in the analysis population (full population analysis).

7.5 Procedure(s) to account for missing or spurious data

Multiple imputation using Chained Equations approach (MICE) will be used to fill in missing data. Ten imputations (M=10) will be chosen to obtain valid inference and reduce sampling variability resulting from the imputation process. Variables with a missing rate above 15% will be excluded and the outcomes will be included in the imputation model. All 10 datasets will be analyzed and combined using Rubin rules.

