3. OBJECTIVES AND OUTCOME MEASURES/ENDPOINTS

It is hypothesised that HIV infection is a risk factor for more severe COVID-19 outcomes and that advanced immunodeficiency as defined by current CD4 T-cell count or CD4 T-cell nadir is a risk factor for more severe COVID-19 outcomes in PLWHIV.

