3.1 Primary objective

1. To describe outcomes of COVID-19 in PLWHIV in comparison to HIV seronegative COVID-19 controls.
2. To identify risk factors (e.g. CD4 cell nadir, current CD4 count, co-morbidities) for severe COVID-19 outcomes within the group of PLWHIV.

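### The 15% missingness exclusion in section 7.5 has no exemption, denominator or fallback, so it could remove the hypothesised CD4 exposures or the named confounder obesity from the primary analyses, or leave them unimputed with no stated handling

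*Combined protocol and SAP*

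**What the plan says.** Section 7.5 first states the general method: "Multiple imputation using Chained Equations approach (MICE) will be used to fill in missing data". It sets ten imputations, pooled by Rubin's rules, and adds: "Variables with a missing rate above 15% will be excluded and the outcomes will be included in the imputation model". Nothing else in the document qualifies this sentence.

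The variables that the rule could reach carry much of the study's purpose:

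- Section 3 gives as a hypothesis that "advanced immunodeficiency as defined by current CD4 T-cell count or CD4 T-cell nadir is a risk factor for more severe COVID-19 outcomes in PLWHIV".
- Section 3.1 makes this the second primary objective: "To identify risk factors (e.g. CD4 cell nadir, current CD4 count, co-morbidities) for severe COVID-19 outcomes within the group of PLWHIV".
- Section 7.3.2 lists among the factors for the second primary analysis "CD4 cell nadir; last CD4 cell count/HIV-RNA before COVID-19 diagnosis (including CD4% and CD4/CD8 ratio) at baseline".
- Section 7.3.2 also names obesity, defined from BMI, and the Appendix 1 comorbidities as adjustment variables in the first primary analysis. Neither is a matching criterion in section 4.1.

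Section 6.2 states that all data are retrospective, taken from site records or existing cohort databases. Laboratory values, which are secondary endpoint 9, are collected only where they exist, within 10 days of the positive test.

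**The concern.** A cut-off that applies to every variable alike treats a hypothesised exposure in the same way as an optional covariate. With 16% of values missing and 84% observed, CD4 nadir could drop out of the analysis that was set up to study it. Obesity could likewise drop out of the adjustment set for the comparison by HIV status. Either change would follow from the state of the records and not from a decision about what the analysis needs.

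The rule also limits the planned imputation to variables with mild missingness. Above 15%, the plan gives no replacement: no complete-case analysis, no sensitivity analysis, and no statement of which group the percentage refers to.

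**Working it through.** The plan derives no figure from the 15% rule, so there is nothing of its own to reproduce. The check is what the rule means in head-counts, and whether its result is determined by the text.

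**Inputs.** 500 cases, 1,000 HIV-positive controls and up to 1,500 HIV-negative controls (synopsis). The rates marked as assumed below are illustrations.

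**1. Trigger, 0.15 × N.**

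- Cases only: 0.15 × 500 = 75.
- People living with HIV: 0.15 × (500 + 1,000) = 225.
- COVID-19 patients at the maximum control number: 0.15 × (500 + 1,500) = 300.

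A variable is excluded when more than that number lack a value.

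**2. The undefined denominator changes the answer for CD4 (assumed rates).**

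- 10% missing in cases and 20% in HIV-positive controls: (50 + 200)/1,500 = 16.7%. Excluded if the groups are pooled; kept if the rate is taken in cases.
- 5% and 20%: (25 + 200)/1,500 = 15.0%. On the boundary, so kept.
- 30% and 5%: (150 + 50)/1,500 = 13.3%. Kept if pooled; excluded if the rate is taken in cases.
- Taken over the whole study of up to 3,000 subjects, CD4 is absent by design in the 1,500 HIV-negative controls: 1,500/3,000 = 50%. Nobody is likely to intend this denominator, but the text does not rule it out.

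**3. Obesity.** With complete BMI in all 500 cases and 1,500 controls, the trigger is passed once more than 300/1,500 = 20% of controls lack weight or height, however good the case data are.

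**4. Laboratory endpoints.** Section 6.1 reports 436 hospitalisations among 1,187 patients, or 36.7%. Take that as the inpatient share of cases, and assume inpatients are complete.

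- Cases alone: 0.15/(1 − 0.367) = 23.7% missing in outpatients reaches the limit.
- After 1:1 inpatient and 1:3 outpatient matching, the outpatient share is (0.633 × 4)/(0.367 × 2 + 0.633 × 4) = 77.5%. The limit is then reached at 0.15/0.775 = 19.4% missing in outpatients.

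This shows how the rule would act if it applies to these endpoints; the text leaves that open.

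**5. The two readings of the sentence.**

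- Excluded from the analysis: CD4 nadir, current CD4 or obesity above the limit leaves the model.
- Excluded from the imputation model only: the variable is not imputed, and the plan does not say whether it is then analysed on complete cases or dropped.

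On either reading a pre-specified variable above 15% gets no imputation and has no stated handling beyond that.

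**The case against.** The strongest reply is that the sentence is ambiguous and the trigger may never be reached. The closing words about the imputation model can govern both verbs, so exclusion from the analysis is not established. No missing rates are given. Section 6.2 attaches an availability qualifier to ethnicity and to laboratory values, but not to weight, height or CD4. People living with HIV attend regular clinic visits (section 6.1), and the last CD4 count is taken with no time window, so one earlier value is enough. More than 15% missing for current CD4 may therefore be unlikely. All of this stands, and it limits the point to what the rule permits.

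A reader might infer several stronger things that the documents do not support:

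- *That the study could not test its hypothesis.* Section 3 names current CD4 or nadir, so losing one would leave the other.
- *That exclusion discards all information, or leaves confounding by obesity wholly uncontrolled.* Section 7.3.1 still summarises every variable on its observed values, and adjustment for age, sex and comorbidities, diabetes among them, would remain.
- *That the laboratory endpoints will be deleted.* The same sentence keeps outcomes in the imputation model, which may exempt them. It does not say so clearly.
- *That ten imputations are efficient enough to make a cut-off pointless.* Relative efficiency, 1/(1 + fraction of missing information/10), measures only the precision lost by using a finite number of imputations. A cut-off usually guards against dependence on the missing-at-random assumption, which that formula does not address.

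It is also fair to say that a threshold fixed in advance on missingness is milder than one chosen after seeing results.

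**Conclusion.** The point holds as a defect in the rule, not as a prediction of what will happen. Applied as written, section 7.5 could remove a hypothesised exposure of the second primary objective or change the adjustment set of the first primary analysis. On the narrower reading it leaves those variables without imputation or stated handling. The trigger is more than 75, 225 or 300 subjects, depending on a denominator that the plan does not define. Whether it is reached cannot be known from the documents. The illustrations for CD4 and obesity rest on assumed rates. The laboratory case has more support, because incomplete collection is foreseen, but it is less certain in another respect, because the outcomes clause may already exempt it. The plan should be changed before the data are analysed; no sample size or power figure depends on it.

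**What to change.** Amend section 7.5 as follows:

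- State that the pre-specified exposures (CD4 nadir, current CD4, HIV-RNA) and the named confounders (BMI, comorbidities) are kept and imputed whatever their missing rate. Age and sex are matching criteria and need no such protection.
- Apply the 15% limit only to optional candidate variables, and say whether exclusion is from the analysis or from the imputation model.
- Define the missing rate within each comparison, with CD4 and HIV-RNA assessed among people living with HIV only, and report it by group.
- Add a complete-case sensitivity analysis, and a missing-not-at-random analysis if missingness is high.
- For laboratory endpoints, state whether the outcomes clause exempts them. Analyse the observed values and report missingness by inpatient and outpatient status. Imputation at any rate should not be required, because missingness in outpatients may depend on severity.

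The cost is SAP wording and a few extra analyses. Data collection and sample size are unchanged. The downside is that results for heavily missing variables lean more on the missing-at-random assumption, which the sensitivity analyses are there to examine.
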